	To compare the effects of graded exercise to passive stretching using ClearPlay© on symptomatic recovery rate following mTBI.	
 • Within-subject analysis of change in symptoms over time using the PCSS, comparing short-term ‘survival rates’ between graded exercise and stretching using Kaplan-Meier analyses for days since concussion.
	Secondary Objectives	Secondary Endpoints
	To compare the safety and tolerability of graded exercise to passive stretching in patients following mTBI.	
 • Adverse events reported from Day 1 through Day 56, including those identified during exercise or passive stretching during the 20 minutes of daily therapy.
To compare symptom resolution following graded exercise compared to passive stretching using ClearPlay© following mTBI.	
 • Within subject analysis of change in the number of subjects who are symptom free at 8 weeks between the 2 groups. Symptom free is defined by subjects having 3 consecutive days of PCSS scores lower than pre-concussion. 
Note: This objective is similar to the primary one, with the primary endpoint being recovery (binary outcome) vs. symptom resolution (continuous variable).
 
 • Determine differences in symptomatic recovery based on gender, baseline scores on the PCSS, baseline athletic fitness (Godin leisure-time exercise questionnaire), the history of injury, a history of migraine, as well as the presence of pre-morbid anxiety. 	
To compare the effects of graded exercise to passive stretching using ClearPlay© on physiologic recovery rate following mTBI.	
 • Within subject analysis of normalization of physiologic measurements obtained during the BCBT comparing data collected on entry to the study on Day 0 vs. follow up on Day 56 including: 
 - Beat to beat BP; • Determine differences in physiologic recovery based on gender, baseline scores on the PCSS, baseline athletic fitness (Godin 	

		leisure-time exercise questionnaire), the history of injury, a history of migraine, as well as the presence of pre-morbid anxiety (BAI; BSI-18; ASI).

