4.2 Study Objectives and Endpoints

The study objectives and endpoints to be evaluated in this study are presented in Table 1.

Table 1: Study Objectives and Endpoints

Objectives	Endpoints
Primary Objectives	Primary Endpoints
To compare the effects of graded exercise to passive stretching using ClearPlay© on symptomatic recovery rate following mTBI.	
 • Within-subject analysis of change in symptoms over time using the PCSS, comparing short-term ‘survival rates’ between graded exercise and stretching using Kaplan-Meier analyses for days since concussion.
Secondary Objectives	Secondary Endpoints
To compare the safety and tolerability of graded exercise to passive stretching in patients following mTBI.	
 • Adverse events reported from Day 1 through Day 56, including those identified during exercise or passive stretching during the 20 minutes of daily therapy.
To compare symptom resolution following graded exercise compared to passive stretching using ClearPlay© following mTBI.	
 • Within subject analysis of change in the number of subjects who are symptom free at 8 weeks between the 2 groups. Symptom free is defined by subjects having 3 consecutive days of PCSS scores lower than pre-concussion. 
Note: This objective is similar to the primary one, with the primary endpoint being recovery (binary outcome) vs. symptom resolution (continuous variable).
 
 • Determine differences in symptomatic recovery based on gender, baseline scores on the PCSS, baseline athletic fitness (Godin leisure-time exercise questionnaire), the history of injury, a history of migraine, as well as the presence of pre-morbid anxiety.
To compare the effects of graded exercise to passive stretching using ClearPlay© on physiologic recovery rate following mTBI.	
 • Within subject analysis of normalization of physiologic measurements obtained during the BCBT comparing data collected on entry to the study on Day 0 vs. follow up on Day 56 including: 
 - Beat to beat BP; • Determine differences in physiologic recovery based on gender, baseline scores on the PCSS, baseline athletic fitness (Godin leisure-time exercise questionnaire), the history of injury, a history of migraine, as well as the presence of pre-morbid anxiety (BAI; BSI-18; ASI).

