To compare the effects of graded exercise to passive stretching using ClearPlay© on accelerating symptomatic vs. physiologic recovery rate following mTBI.	
 • Combined analysis of data from the two secondary analyses outlined above to confirm or refute a significant correlation between symptom resolution (defined by subjects having 3 consecutive days of PCSS scores lower than pre-concussion) and physiologic measurements obtained during the BCBT comparing data obtained on entry to the study on Day 0 vs. follow up on Day 56 including: 
 - Beat to beat BP;

Objectives	Endpoints
To develop a composite physiologic metric to predict the magnitude and duration of ongoing post-concussive symptoms.	
 • Develop predictive modeling algorithms to establish a composite physiologic metric predictive of subjects becoming symptom free (as defined by subjects having 3 consecutive days of PCSS scores lower than pre-concussion) using data derived from baseline physiologic testing with: 
 - BCBT - Ice bucket testing - ClearPlay© testing
To develop a composite neuropsychologic metric to predict the magnitude and duration of ongoing post-concussive symptoms.	
 • Develop predictive modeling algorithms to establish a composite neuropsychologic metric predictive of subjects becoming symptom free (as defined by subjects having 3 consecutive days of PCSS scores lower than pre-concussion) using data derived from baseline neuropsychologic testing with the following instruments: 
Attention (CAARS)
 
 - Depression (CES-D) - Anxiety (BAI; BSI-18; ASI).
To develop a composite blood-based or saliva biomarker metric to predict the magnitude and duration of ongoing post-concussive symptoms.	
 • Analysis of biomarkers at baseline testing including: 
 - Structural proteins [t-tau, NF-L, GFAP and UCH-L1] - Inflammatory cytokines [IL-6, IL-10 and TNFα] - SNPs [APO-E4, BDNF, and NFkB]

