9.6.2 Neuropsychology Testing Analysis

Neuropsychology testing will be assessed using the patient reported outcomes and will be summarized at each protocol scheduled time point by treatment group, using either summary statistics or frequency tabulations, as applicable to the type of data. Changes from baseline will also be presented where applicable.

Results of the cold pressor test, whiplash test and BCBT will be summarized at each protocol scheduled time point by treatment group, using either summary statistics or frequency tabulations, as applicable to the type of data. Changes from baseline will also be presented where applicable.

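### Two secondary objectives compare exercise with stretching on physiologic recovery, but the analyses stated for them contain no treatment contrast

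*Protocol*

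**What the plan says.** Table 1 in Protocol 4.2, repeated in the synopsis, gives as a secondary objective: "To compare the effects of graded exercise to passive stretching using ClearPlay© on physiologic recovery rate following mTBI". The analysis beside it reads: "Within subject analysis of normalization of physiologic measurements obtained during the BCBT comparing data collected on entry to the study on Day 0 vs. follow"-up on Day 56, with beat-to-beat blood pressure (BP) as the only measure listed. A second bullet looks for differences in physiologic recovery by gender, baseline PCSS, fitness, injury history, migraine and anxiety. Treatment arm is not on that list.

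The next objective compares the arms on symptomatic versus physiologic recovery. Its analysis is: "Combined analysis of data from the two secondary analyses outlined above to confirm or refute a significant correlation between" symptom resolution and the BCBT measurements. Again no arm is named.

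Two other rows of the same table do name the contrast. The primary row ends "between graded exercise and stretching using Kaplan-Meier analyses for days since concussion". The symptom-free row reads "Within subject analysis of change in the number of subjects who are symptom free at 8 weeks between the 2 groups".

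In Section 9, the logistic, log-rank and Cox analyses of 9.6 concern symptom resolution. BCBT enters 9.6 only through the heart-rate response used to check that randomisation balanced the groups. Section 9.6.2 says: "Results of the cold pressor test, whiplash test and BCBT will be summarized at each protocol scheduled time point by treatment group", with changes from baseline added where applicable.

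**The concern.** The objective asks whether physiology recovers better with exercise than with stretching. The stated analysis asks whether BCBT readings differ between Day 0 and Day 56. Those are different null hypotheses, and in a condition that mostly resolves by itself the second can be false while the first is true. Section 9.1 assumes 80% symptom resolution under stretching, so the protocol itself expects much symptomatic recovery without exercise.

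Three things are at stake. An 8-week improvement shared by both arms could be presented as support for exercise. The arms could be compared informally, by noting significance in one and not in the other, which is not a test of the arms. And a real exercise effect on physiology could go unseen, because both arms would show clear change over time. The correlation row has a different weakness: whatever its result, it says nothing about exercise versus stretching.

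**Working it through.** **1. Is the contrast supplied elsewhere?**

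| Place | Objective or purpose | Comparator stated |
|---|---|---|
| Table 1, primary row | Arms, symptomatic recovery | Exercise vs stretching |
| Table 1, symptom-free row | Arms, symptom resolution | Between the two groups |
| Table 1, physiologic row | Arms, physiologic recovery | Day 0 vs Day 56 |
| Table 1, symptomatic vs physiologic row | Arms, both recoveries | Correlation; no arm |
| 9.6 | Symptom resolution; baseline balance | Arms, but not for Day 56 BCBT |
| 9.6.2 | BCBT results and changes | By group, descriptive |

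No between-arm analysis of Day 56 BCBT is stated anywhere in the protocol.

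**2. The plan's own figure.** The only design figures are for symptom resolution (9.1): 80% vs 93%, alpha 0.05, power 90%, 316 subjects. A two-sided comparison of proportions with continuity correction gives 159 per arm, 318 in total, which agrees closely. Nothing is stated for the physiologic objectives, so the inputs below are partly assumed.

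**3. Inputs.**
- From 9.1: 200 per arm and 15% attrition, so 200 × 0.85 = 170 per arm and 340 pooled; alpha 0.05, taken as two-sided because the sides are not stated.
- Assumed: natural change d, in units of the SD of change, equal in both arms (no arm effect).

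**4. Within-subject test, no arm effect.** Rejection probability ≈ Φ(d√n − 1.96), ignoring the negligible opposite tail.

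Pooled, √340 = 18.44:
- d = 0.1: Φ(1.844 − 1.96) ≈ 45%
- d = 0.2: Φ(3.688 − 1.96) ≈ 96%
- d = 0.3: Φ(5.532 − 1.96) ≈ 100%

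Exercise arm alone, √170 = 13.04:
- d = 0.1: Φ(1.304 − 1.96) ≈ 26%
- d = 0.2: Φ(2.608 − 1.96) ≈ 74%
- d = 0.3: Φ(3.911 − 1.96) ≈ 97%

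**5. Between-arm test, same data.** The expected difference in change is zero, so the test rejects 5% of the time whatever d is. Simulation (4,000 trials, 170 per arm) gave 5.1%, 4.7% and 5.2% at d = 0.2, 0.3 and 0.5.

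**6. Significant with exercise, not with stretching, when the arms are equal.** The probability is p(1 − p), with p the one-arm figure. At d = 0.2: 0.741 × 0.259 ≈ 19%.

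**7. When exercise does work.** Assume 0.5 SD natural change, an extra 0.3 SD from exercise, and a Day 0/Day 56 correlation of 0.5. The SD of change is √(2(1 − 0.5)) = 1, so raw and change SDs coincide.
- Within-arm tests: significant in both arms in essentially every trial, so they do not reveal the effect.
- Between-arm change score: SE = √(2/170) = 0.108; 0.3/0.108 = 2.77; power Φ(2.77 − 1.96) ≈ 79%.
- Between-arm ANCOVA: SE = 0.108 × √(1 − 0.5²) = 0.094; 0.3/0.094 = 3.19; power Φ(3.19 − 1.96) ≈ 89%.

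**8. The correlation.** Equal mean improvement in everyone produces no correlation. If subjects who resolve really are those whose physiology changes, with true correlation 0.1, 0.2 or 0.3, Fisher's z with n = 340 gives significance in about 45%, 96% and 100% of trials with no arm effect. That is power to find a real association. It carries no information on treatment.

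**The case against.** The strongest reply is that the table describes an endpoint, not a test. It sits beside a comparative objective, and the primary and symptom-free rows also say within subject while comparing the arms. The row could mean each subject's change, compared between arms. The protocol states no null hypothesis or success rule for this endpoint, 9.6 leaves the full efficacy presentation to the SAP, and 9.6.2 does set out BCBT results and changes by group.

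Part of this stands. A reader might infer that the protocol would declare the objective met because subjects improved; it does not say so. But the rows that compare arms state that contrast, while the physiologic row states a different one, Day 0 against Day 56. Section 9.2 has the SAP implement the protocol's principal features, and the comparator is one of them. This is a comparator stated wrongly, not detail left for later.

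A second reply is that 2.5 calls physiologic normalization diagnostic/prognostic, and 3.2 lists no physiologic arm comparison. For a prognostic aim, within-subject change and a correlation are reasonable. That is fair, but Table 1 and the synopsis word the objectives as treatment comparisons, so the sections need reconciling either way.

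Third, the size of natural change is assumed. The 80% in 9.1 is symptom resolution, and 2.1 says symptomatic recovery cannot reliably be shown to coincide with physiologic recovery. This stands and limits the numbers.

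**Conclusion.** The point holds in a limited form. Two comparative secondary objectives are paired with analyses that contain no treatment contrast, and the protocol supplies none elsewhere. As written, the within-subject analysis cannot attribute physiologic recovery to exercise. With no arm effect it rejects about 45%, 96% and 100% of the time (pooled, 170 per arm) for natural changes of 0.1, 0.2 and 0.3 SD of change, against 5% for a between-arm test. These figures rest on an assumed natural change that is equal in the two arms, and on two-sided alpha 0.05.

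Two stronger readings are not supported. A reader might infer that natural recovery alone guarantees a positive within-subject result whatever exercise does. That depends on the size of natural change: at 0.1 SD the rate is 45% pooled and 26% in one arm, well above 5% but far from certain. A reader might also infer that natural recovery makes the correlation falsely positive. It does not; the correlation is only uninformative about exercise.

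The primary analysis and the sample size are unaffected. The text should be corrected before the SAP carries it forward.

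**What to change.** In Table 1, the synopsis and 9.6:

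- State the physiologic endpoint as the between-arm difference (graded exercise minus passive stretching) in Day 56 BCBT beat-to-beat BP, by ANCOVA adjusted for the Day 0 value and the randomisation strata (site; PCSS below 30 or 30 and above), with a 95% CI, analysed as randomised. Say which direction of difference counts as recovery, since Day 56 BP replaces the undefined term normalization.
- Amend 9.3.3, which groups autonomic data by the therapy actually received; otherwise it conflicts with an as-randomised analysis.
- Keep the Day 0 to Day 56 changes within each arm as descriptive.
- Label the symptom-physiology correlation a prognostic association, adjusted for arm. It is not evidence that exercise speeds either recovery.
- Reconcile the objective wording with 2.5 and 3.2. If the sponsor's aim is prognostic only, reword the Table 1 and synopsis objectives so that they no longer promise an arm comparison.

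The cost is wording in those sections and one extra model. Table 5 already schedules the BCBT at Day 0 and Day 56, so no new data are needed. The downside is that the physiologic result will be significant less often than under the within-subject test.

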The current standard of care for patients with mTBI is cognitive and physical rest. However, a recently conducted randomized control trial suggests that the implementation of exercise activity as opposed to physical and cognitive rest during the initial period of injury accelerates recovery.²⁰ Sub-symptom threshold aerobic exercise, has been shown to improve autonomic function as reflected by non-invasive measures such as heart rate variability (HRV),²¹ and to accelerate recovery following concussion.

It is anticipated that results from our study, in combination with those evolving from similar research studies now underway in Australia as well as the US, will provide support for decision making by physicians, trainers, and other clinicians during the days/weeks following concussion, including what activities should be avoided, what therapies can accelerate recovery, and when the brain has recovered so that it is safe to resume sport or work.

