7.4.2 Godin Leisure Time Exercise Questionnaire

The Godin leisure-time exercise questionnaire is a well validated activity scale. It asks subjects to rate their exercise as either mild, moderate or strenuous, and will provide an indication for how each subject perceived the exercise allocated to them.

This scale will be used to identify the degree of self-reported athletic exertion of each subject weekly.

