7.4.3 Beck Anxiety Inventory

The Beck Anxiety Inventory (BAI) enables clinicians to measure the severity of anxiety in adolescents and adults. The BAI has been found to discriminate well between anxious and non-anxious diagnostic groups in a variety of clinical populations.

Subjects respond to 21 items rated on a scale from 0 to 3, each item is descriptive of subjective, somatic, or panic-related symptoms of anxiety.

This scale will be used as a predictor of anxiety-induced prolongation of PPCS.

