8 STUDY SCHEDULE OF EVENTS

8.1 Order of Assessments

The order of assessment for each subject is dependent on their assigned subject identification numbers. Refer Table 4 for detail.

Table 4: Order of Assessments :

Subjects Assigned to ODD numbered subject identification numbers	Subjects Assigned to EVEN numbered subject identification numbers
Biomarker sample collection	Biomarker sample collection
Ice Bucket Test	ClearHeart©
Neuropsychology Testing (CAARS, CES-D, BAI, ASI [Pre/Post mTBI], BSI-18 [Pre/Post mTBI]).	Neuropsychology Testing (CAARS, CES-D, BAI, ASI [Pre/Post mTBI], BSI-18 [Pre/Post mTBI]).
Neurologic Evaluation	Neurologic Evaluation
ClearNeck©	ClearNeck©
ClearHeart©	Ice Bucket Test
Buffalo Concussion Bike Test	Buffalo Concussion Bike Test
Randomize subject to Exercise or Stretching Group	
Dispense i-touch or i-phone with appropriate software loaded (whether randomized to graded exercise vs. passive stretching). Subject to enter test PCSS and Godin score via ClearPlay App©; to ensure subject is able to use this App.	Dispense i-touch or i-phone with appropriate software loaded (whether randomized to graded exercise vs. passive stretching). Subject to enter test PCSS and Godin score via ClearPlay App©; to ensure subject is able to use this App.
Adverse Events	Adverse Events

Post-study survey to be completed at Day 56 only

Abbreviations: ASI = Anxiety Sensitivity Index, BAI = Beck Anxiety Inventory, BESS = Balance Error Scoring System, BSI = Brief Symptom Inventory, CAARS = Conners' Adult Attention Deficit Hyperactivity Disorder Rating Scale, CES-D = Center for Epidemiologic Studies - Depression Scale, DNA = deoxyribonucleic acid, PCSS = Post-Concussion Symptom Scale, RNA = ribonucleic acid, VOMS = Vestibular-Oculomotor Screening

Table 5: Schedule of Events

Study Assessments	Baseline Visit		Therapy Period	Telephone Safety Visit	Follow-Up/ET
	Day 0 (within 3 to 14 days of concussion)		Day 1 to Day 55	Day 14, Day 28, Day 42 (± 2 days)	Day 56 (± 3 days)
	Screening Evaluation	Study Evaluation			
Study Assessments					
Informed consent	X				
Allocate unique subject study identification	X				
Inclusion/exclusion criteria review	X				
Demographic data	X				
Medical and medication history	X				
Review of CT or MRI (if obtained)	X				
Height and weight ^a	X				X
Subject Completed Questionnaires					
Post-Concussion Symptom Scale (pre- and post-mTBI)		X	X		
Godin leisure time exercise questionnaire ^b		X	X		X

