9.6 Efficacy Analysis

The full presentation of the analysis of efficacy data will be presented in the SAP.

For all subjects, daily reported PCSS scores collected from ClearPlay© mobile application will be utilized to determine the resolution of symptoms. The resolution of symptoms is defined as a symptom-severity score of less than each subject's pre-injury PCSS score for 3 consecutive days. To assess differences in the probability of symptom resolution between graded exercise and passive stretching during the 8 weeks of therapy, both unadjusted and adjusted logistic regression models will be used. The primary outcome of the study will be to confirm or refute the superiority of sub-threshold aerobic exercise versus passive stretching to result in resolution of symptoms following mTBI. Confounders for the adjusted models will include age, gender, anxiety at baseline, history of migraine, cardiovascular fitness, the presence or absence of neurologic findings, and site of enrollment.

The survival probability will be compared using Kaplan-Meier (log rank test) analyses between the 2 treatment arms. Cox proportional hazards regression models will be used to evaluate the differences in time to symptom resolution. Adjusted treatment effects will be estimated in Cox proportional hazards regression models, controlling for the variables listed above. To identify that our randomization strategy was effective, analysis of variance will be used to assess for group-wise differences in age, days since injury to initial visit, initial PCSS score, resting HR, and Δ HR during the BCBT and resting BP and Δ BP during the ice bucket test on Day 1. Non-parametric tests of medians will be used to compare the non-normally distributed variable duration of clinical recovery. Chi-squared tests will be used to assess group-wise differences in gender, history of concussions, and incidence of PPCS.

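### The BAI is listed as a measure of pre-morbid anxiety and the Godin as the measure of baseline athletic fitness, but neither has a pre-injury version or reference period at Day 0

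*Protocol*

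**What the plan says.** Table 1 in section 4.2 contains two secondary endpoints that examine differences in recovery by subject characteristics, one for symptomatic and one for physiologic recovery. Both name "baseline athletic fitness (Godin leisure-time exercise questionnaire") as a factor. Both also name pre-morbid anxiety, but only the physiologic-recovery endpoint attaches instruments to it: "as well as the presence of pre-morbid anxiety (BAI; BSI-18; ASI").

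All of these questionnaires are given at the baseline visit, which Table 5 places at "Day 0 (within 3 to 14 days of concussion"). Table 4 lists the anxiety instruments as "BAI, ASI [Pre/Post mTBI], BSI-18 [Pre/Post mTBI"]. Table 5 likewise marks the PCSS, BSI and ASI as pre- and post-mTBI, and leaves the BAI and Godin rows without that marking.

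Section 7.4.2 says of the Godin: "This scale will be used to identify the degree of self-reported athletic exertion of each subject weekly". It adds that the form shows how subjects perceived the exercise allocated to them. Section 7.4.3 says of the BAI that "each item is descriptive of subjective, somatic, or panic-related symptoms of anxiety".

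Section 9.6 adjusts the logistic and Cox models for several variables, among them "anxiety at baseline, history of migraine, cardiovascular fitness". It names no instrument for anxiety or for fitness.

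**The concern.** Pre-morbid anxiety is by definition a state that precedes the injury. Fitness is evidently meant in the same way. Section 2.1 lists athleticism beside sex, age, prior concussions and migraine as a contributor to symptom severity and duration, and section 2.5 suggests that athletes may recover faster because of their conditioning.

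A BAI completed after a concussion asks about anxiety, including bodily symptoms, in a subject who qualified by having a new or worsened symptom such as dizziness, insomnia or irritability (inclusion criterion 3). A Godin completed at the same visit may describe a period of reduced activity, since section 2.1 states: "The current standard of care for patients with mTBI is cognitive and physical rest".

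If so, both scores partly track how ill the subject was at entry and how long ago the injury occurred. An association of low fitness or high anxiety with slow recovery could then be read as the effect of a pre-existing trait when it is partly the effect of the injury itself.

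**Working it through.** The plan states no figure on this point, so the check is a comparison of sections, followed by an illustration under stated assumptions.

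**Anxiety.** Table 1 names three instruments as pre-morbid.
- BSI-18: pre- and post-mTBI in Tables 4 and 5.
- ASI: pre- and post-mTBI in Tables 4 and 5.
- BAI: no pre-mTBI version in either table; completed at Day 0 and Day 56.

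Two of the three instruments therefore supply a retrospective pre-injury rating and one does not. The schedule treats the reference period as important: a Table 5 footnote specifies that the Day 56 questionnaires it marks are to be answered for the subject's current condition. The BAI is the one instrument whose label in Table 1 does not match its scheduling.

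**Fitness.** The Godin's uses and placement are as follows.
- Table 1: source of baseline athletic fitness.
- Section 7.4.2: weekly exertion and perception of the allocated exercise.
- Section 5.3.1: detection of subjects who exercise beyond what is prescribed.
- Table 5: Day 0, therapy period and Day 56, given weekly, with no pre-mTBI marking.
- Table 4: absent from the steps before randomisation. It appears only afterwards, as a test entry to confirm that the subject can use the app.

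Apart from Table 1, the described uses concern current activity. No section gives the Day 0 form a reference period, and the appendices list the questionnaires by title only.

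**Illustration of size.** Assume the form recalls the last L days, and let d be the days from concussion to Day 0. The share of the recall period lying after the injury is min(d, L) / L.
- L = 7: d = 3 gives 3/7 = 43%; d = 6 gives 6/7 = 86%; d = 7 to 14 gives 100%.
- L = 14: d = 3 gives 3/14 = 21%; d = 14 gives 14/14 = 100%.
- L = 28: d = 3 gives 3/28 = 11%; d = 14 gives 14/28 = 50%.

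Days 3 to 14 are 12 possible entry days. With L = 7, days 7 to 14 are 8 of them, and 8/12 = 67% if entry is spread evenly. Both the recall period and the even entry are assumptions. In each of the three cases some post-injury time is included and the share does not fall as d increases. A form asking about a usual week would behave differently, but would still need to say whether the weeks before or after the concussion are meant.

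**Treatment comparison.** Therapy runs from Day 1, so it cannot have altered scores obtained at Day 0. The unadjusted logistic model and the log-rank test in section 9.6 use neither the BAI nor the Godin.

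**The case against.** Several stronger conclusions are tempting, and the protocol does not support them.

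A reader might infer that the pre-morbid anxiety objective as a whole measures effects of the injury. It does not have to: the pre-mTBI BSI-18 and ASI are already scheduled, and section 7.1.2 also collects psychiatric history. Nor are both endpoints tied to the BAI, since the symptomatic-recovery endpoint names no anxiety instrument. The BAI's other uses are sound with a Day 0 score: as a predictor of prolonged symptoms (section 7.4.3), as part of the baseline neuropsychologic metric (Table 1), or as the covariate for anxiety at baseline.

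A reader might also infer that the adjusted models fail to control for fitness. Section 9.6 does not say that the Godin is the source of that covariate. The Day 0 bicycle test (BCBT) also yields exercise data, and the choice of instrument may properly be left to the SAP. The BCBT is, however, itself a post-injury test that can end on symptom exacerbation, so it would not supply pre-injury fitness either.

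On the Godin, Table 1 says baseline rather than pre-injury, the form's items are not shown, and how often a form is given does not fix the period it asks about. Post-injury rest cannot be assumed for everyone, because sections 2.2 and 2.6 note that active rehabilitation is now endorsed. Table 4 may also simply be incomplete: the PCSS, too, appears there only after randomisation, although randomisation is stratified on its baseline value. All of this stands, and it makes distortion of the Godin score a risk rather than an established fact. It does not remove the gap, because nothing in the protocol fixes the reference period or places the Godin before allocation in an open-label trial.

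**Conclusion.** The point holds in limited form. The BAI is mislabelled as a pre-morbid measure in the physiologic-recovery endpoint, which follows directly from Tables 1, 4 and 5. The Godin, as scheduled, may reflect reduced activity after the injury. That rests on the absence of any stated reference period, together with the rationale's treatment of athleticism as a prognostic trait.

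The harm is to the interpretation of the anxiety and fitness factors in the secondary endpoints, and of the section 9.6 fitness covariate if the Godin is used for it. The unadjusted treatment comparison is untouched. The size cannot be determined from the protocol; the 67% figure illustrates one assumed recall period and entry pattern and is not an estimate for this trial.

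The change is worth making in the protocol. A SAP could select among anxiety scores already collected, but it could not recover a pre-injury Godin that subjects were never asked to complete.

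**What to change.** 1. In Table 1, define pre-morbid anxiety from the pre-mTBI BSI-18 and ASI, for both endpoints, and treat the Day 0 BAI as current anxiety at baseline. Alternatively, keep the BAI in the definition and add a pre-mTBI BAI at Day 0 in Tables 4 and 5.
2. In Tables 4 and 5, have the Day 0 Godin completed before randomisation for the usual week before the concussion, and label it pre-mTBI as for the PCSS, BSI and ASI.
3. Use that score as baseline athletic fitness, and for the fitness covariate in section 9.6 if the Godin is its source. Name the covariate's source in either case.
4. Keep the weekly Godin for monitoring exertion.

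The cost is one instruction line on an existing questionnaire and wording changes in Tables 1, 4 and 5 and section 9.6, with no new visit or instrument. Adding a pre-mTBI BAI would mean one further completion of a 21-item form. The small downside is recall error, which the trial already accepts for the PCSS, BSI-18 and ASI.
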